1 PROTOCOL SUMMARY

1.1 SYNOPSIS

Title	NIcotinamide Riboside in SARS-CoV-2 pAtients for reNAl protection (NIRVANA)			
Study Description	A pilot, double-blind, placebo-controlled, multicenter, interventional clinical trial with oral nicotinamide riboside (NR) 500 mg (versus placebo) twice daily for a total of 10 days in hospitalized participants with COVID-19.			
Objectives	Primary			
	 To determine the effect of nicotinamide riboside (NR) on whole blood NAD+ levels in hospitalized patients with COVID-19 infection and AKI during the 10-day intervention period; To evaluate the safety of NR in patients with COVID-19 infection and AKI during the 10-day intervention period; 			
	Secondary			
	 To determine the effect of NR on changes in area under curve (AUC) serum creatinine from baseline during the 10-day intervention; To determine the effects of NR on serum creatinine AUC, dialysis, and death with an ordinal categorical outcome having four categories (labeled 1, 2, 3, 4), defined as, in order from least to most severe disease, 1. Serum creatinine AUC < median, 2. Serum creatinine AUC ≥ median, 3. Dialysis, 4. Death during the 90d period post randomization; To determine the effect of NR on MAKE (Major Adverse Kidney Events; composite criteria defined as development or progression of chronic kidney disease, the initiation of long-term dialysis, or death from any cause) at 30d and 90d post randomization; To determine the effect of NR on degree of kidney impairment defined with estimated glomerular filtration rate (eGFR) and proteinuria at 30d and 90d post randomization; 			
	Exploratory			
	• To determine the relationship of whole blood NAD+ levels with AUC creatinine and surrogate markers of AKI such as kidney injury molecule- 1 (KIM-1) and neutrophil gelatinase-associated lipocalin (NGAL);			
Endpoints	Primary			
	 Rates of change in whole blood NAD+ level from baseline to day 10 in NR compared to Placebo. Safety of NR in hospitalized patients with COVID-19 and AKI (defined as the occurrence of at least one serious adverse event of grade 3 or higher or the occurrence of thrombocytopenia (>25% decline in blood platelet count from baseline value). 			

	Secondary				
	 Rates of change in AUC serum creatinine benchmarked to baseline from baseline to day 10 in NR compared to Placebo; An ordinal categorical outcome with four categories (labeled 1, 2, 3, 				

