	4), defined as, in order from least to most severe disease, 1. Serun creatinine $AUC < median$, 2. Serum creatinine $AUC \ge median$, 3. Dialysis, 4. Death;				
	• Time to first occurrence of MAKE (doubling of serum creatinine, the initiation of long-term dialysis, or death from any cause) at 30 d and 90 d post randomization;				
	• Kidney function defined by eGFR and proteinuria at 30d and 90d post randomization.				
	Exploratory				
	• Correlations between whole blood NAD+, AUC serum creatinine, and AKI surrogate markers of AKI such as KIM-1 and NGAL;				
Study Population:	Participants will be >18 years old and admitted to hospital with a laboratory diagnosis of COVID-19 infection and AKI				
Phase:	Phase 2				
Description of	The study is a multicenter study with University of Texas Health San Antonio				
Sites/Facilities	(UTHSA) as the coordinating site. The three recruiting sites are: University				
Enrolling	Hospital affiliated with UTHSA, Icahn School of Medicine at Mount Sinai,				
Participants:	New York, NY and Harborview Medical Center/University of Washington, Seattle, WA				
Description of	The intervention for this clinical trial is Niagen®, a nicotinamide riboside,				
Study	an over the counter nutritional supplement				
Intervention:					
Study Duration	Estimated 2 years				
Participant	The estimated time required for this study will be up to 90 days after				
Duration:	consenting to study protocol. A total of up to 10 visits will occur during the				
	initial 10 days with two follow-up visits -30 days and 90 days from				
	enrollment date.				

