1.3 SCHEDULE OF ACTIVITIES (SOA)

Table 1. Schedules of activities

Study Period \Rightarrow	Scree	Treatment Period					Follow-up						
Visit Encounter \Rightarrow	Visit	Visit	Visit	Visit	Visit	Visit	Visit	Visit	Visit	Visit	Visit	Visit	Visit
Procedure	0/	1/	2/	3/	4/	5/	6/	7/	8/	9/	10/	11/	12/
Troccuure	Day	Day	Day	Day	Day	Day	Day	Day	Day	Day	Day	Day	Day
	0	1	2	3	4	5	6	7	8	9	10	$30\pm$	90
		(Base line)*										3	±3
Eligibility criteria	Х												
Informed consent	Х												
Demography	Х												
Medical history	Х												
Concomitant	Х	Х	Х	Х	Х	Х	Х	Х	Х	Х	Х	Х	Х
medications ¹													
Vital signs		Х	Х	Х	Х	Х	Х	Х	Х	Х	Х	Х	Х
Physical	Х	Х	Х	Х	Х	Х	Х	Х	Х	Х	Х	Х	Х
examination													
STUDY INTERVEN	TION												
Randomization ²		Х											
Study drug		Х	Х	Х	Х	Х	Х	Х	Х	Х	Х		
administration ³													
STUDY PROCEDU	RES												
APACHE-II	Х	Х	Х	Х	Х	Х	Х	Х	Х	Х	Х		
Endpoint		Х	Х	Х	Х	Х	Х	X	X	Х	Х	Х	Х
assessment													
AE assessment		Х	Х	Х	Х	Х	Х	Х	Х	Х	Х	Х	Х
Respiratory	Х	Х	Х	Х	Х	Х	Х	Х	Х	Х	Х		
parameters ⁴													
Mortality, ICU	Х	Х	Х	Х	Х	Х	Х	Х	Х	Х	Х	Х	Х
transfer, length of													
stay													
Urine output ⁵		Х	Х	Х	Х	Х	Х	Х	Х	Х	Х		
CLINICAL LABOR	ATORY	7									-	-	
Blood analysis ⁶		Х	Х	Х	Х	Х	Х	Х	Х	Х	Х	X	X₽
SAFETY LABORA	ΓORY												
Blood analysis ⁷		Х	Х	Х	Х	Х	Х	Х	Х	Х	Х	Х	Х
RESEARCH LABO	RATOR	Y and R	EPOSI	TORY									
Blood and urine ⁸		Х	Х	Х	Х	Х	Х	Х	Х	Х	Х	Х	Х

APACHE-II, Acute physiology and chronic health evaluation II; AE, adverse events; ICU, Intensive care unit;

* Baseline (Day 1) assessments should be performed prior to study drug administration;

¹ Includes all inhospital and home medications (standard of care treatment, prescription, over-the-counter, supplements);

²Dosing of the first study drug will be administered as soon as possible (within 6 hours of obtaining consent and negative pregnancy test for women with childbearing potential);

³ Participants who will be discharged or leave hospital before Day 10 intervention will be provided with study pills for the remaining days.

⁴ Respiratory rate, FiO₂, O₂ saturation, ventilator parameters, if applicable and participant is hospitalized;

⁵ Urine output data based on medical records or from first morning urine collections if discharged from hospital;

⁶Any laboratory tests performed as part of routine clinical care within the specified visit day may be used for safety laboratory testing by extracting values from the EHR;

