2.3 RISK/BENEFIT ASSESSMENT

2.3.1 KNOWN POTENTIAL RISKS

The study drug NR may not prevent or treat the disease, or the condition of the participant or disease may worsen, but there is currently no accepted standard of care to prevent or treat AKI. As with any research study, there is a potential for side effects to occur with the administration of the study drug. All participants will be closely monitored on a daily basis for adverse events (AEs) defined as changes in health condition and laboratory parameters from baseline (Day 1). Few side effects have been identified for the use of NR, but the side effects that have been reported such as nausea, back soreness and muscle soreness have been typically mild [8].

NR is a formal precursor of NAD+ and naturally present in certain foods including milk. After absorption, NR enters the cell, and is metabolized into nicotinamide mononucleotide (NMN) by a phosphorylation step catalyzed by the nicotinamide riboside kinases (NRKs). NMN is subsequently converted to NAD by nicotinamide nucleotide adenylyltransferases (NMNAT1-3). However, the quantities in foods are quite low, and probably do not exceed the low micromolar range [37]. In the USA, NR is considered as GRAS or Generally Recognized as Safe for use in food products which supports its rapid implementation as a drug-like therapy [17].

NR has been demonstrated to be well-tolerated with mild, if any side effects reported using variables doses from 100 mg/day up to 2000 mg/day [8, 11, 12]. The current study intervention is 1000 mg/day administered as 500 mg twice a day.

NR was recently evaluated in a single center, double blind, placebo-controlled, and crossover study in which 12 elderly participants received 500 mg NR twice a day for 21 days. In this study NR was well tolerated without any SAE including no changes in hematological and clinical biochemistry safety parameters – i.e., renal, liver, and thyroid functions [14]. The reported symptoms included nausea, flushing, leg cramps and increased bruising in the NR group and headache, skin rash, flushing, fainting and drowsiness in the placebo group [7].

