 baseline during the 10-day intervention; To determine the effect of NR on serum AUC, dialysis, and death with an ordinal categorical outcome with four categories (labeled 1, 2, 3, 4), defined as, in order from least to most severe disease, 1. Serum creatinine AUC < median, 2. Serum creatinine AUC ≥ median, 3. Dialysis, 4. Death; To evaluate the effect of NR on on MAKE (composite criteria defined as development or progression of chronic kidney disease), the initiation of long-term dialysis, or death from any cause) at 30d and 90d post randomization. To determine the effect of NR on kidney function defined by eGFR and proteinuria at 30d and 90d post randomization. 	 outcome with four categories (labeled 1, 2, 3, 4), defined as, in order from least to most severe disease, 1. Serum creatinine AUC in the first tertile, 2. Serum creatinine AUC in the second tertile, 3. Serum creatinine AUC in the third tertile, 4. Death; Time to first occurrence of MAKE defined as doubling of serum creatinine, the initiation of long-term dialysis, or death from any cause at 30 day and 90 day post randomization; Kidney function defined by estimated glomerular filtration rate (eGFR) and proteinuria at 30d and 90d post randomization. 	 days of intervention and benchmarked to baseline, has been linked to reduced progression of chronic kidney disease (CKD). The ordinal categories address the hierarchy of increase in severity as has been used in recent COVID-19 studies as per the World Health Organization clinical progression scale [57, 58] AKI may progress to CKD which is associated with need for dialysis and increased mortality.
• To determine the relationship of whole blood NAD+ levels with AUC creatinine and surrogate markers of AKI such as kidney injury molecule-1 (KIM-1) and neutrophil gelatinase- associated lipocalin (NGAL);	• Correlations between whole blood NAD+, AUC serum creatinine, and surrogate markers of AKI such KIM1 and NGAL;	 AUC of serum creatinine is a direct assessment of the duration and severity of AKI; KIM-1 and NGAL are promising surrogate urinary biomarkers of AKI however, their clinical utility in COVID-19 patients with AKI is not known;

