The primary analysis will be based on a cumulative logit model for ordinal data of the primary outcome with terms for treatment, age, gender, clinical site, and baseline serum creatinine. The proportional odds assumption will be tested with a score statistic and empirical logit plots. If the proportional odds assumption is violated then the analysis will be conducted under a partial proportional odds assumption. Under a partial proportional odds assumption, three odds ratios will be estimated; if evidence suggests that the proportional odds assumption holds, a single odds ratio will summarize the treatment effect. In either case, the odds ratio estimate(s), 95% confidence interval(s), and p-value(s) will be reported. Further study will be indicated if the p-value for any treatment effect suggesting benefit in the NR arm is less than or equal to 0.05.

SECONDARY END POINT: Major Adverse Kidney Events (MAKE)

The null hypothesis is H₀:HR=1 where HR is the ratio of the hazard of MAKE with NR treatment to the hazard of MAKE with Placebo treatment. We expect that HR will be less than 1. MAKE is defined as Yes if a doubling of serum creatinine (from baseline), the initiation of long-term dialysis, or death from any cause is observed, and No otherwise. Treatment arms will be compared with regard to the time to the first occurrence of MAKE over the entire duration of the study from baseline to 90 days post-randomization with proportional hazard models of time to MAKE in terms of treatment without and with adjustment for age, race, clinical site, baseline

serum creatine. The coefficients, standard errors and 95% confidence intervals and corresponding hazard ratios will be reported without and with adjustment for covariates. The proportional hazards assumption will be assessed with Schoenfeld residuals and log survival plots. The unadjusted model will be graphically summarized with overlaid Kaplan Meier curves and the p-value for the corresponding log rank test. Covariate interactions with treatment will be of interest and will be explored.

SECONDARY END POINT: Kidney impairment as indicated by eGFR and proteinuria at 30 and 90 days

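### The MAKE objective is CKD development or progression, but its creatinine component counts a first doubling, most naturally from Day 1, and so measures further AKI worsening rather than CKD at Day 30 or 90

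*Combined protocol and SAP*

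**What the plan says.** **Objective.** Section 1.1 describes MAKE as "composite criteria defined as development or progression of chronic kidney disease, the initiation of long-term dialysis, or death from any cause". The objective in Table 2 (Section 3) has the same components, and the justification column adds that "AKI may progress to CKD which is associated with need for dialysis and increased mortality".

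**Endpoint.** Section 1.1 lists "Time to first occurrence of MAKE (doubling of serum creatinine, the initiation of long-term dialysis, or death from any cause". Table 2 has "Time to first occurrence of MAKE defined as doubling of serum creatinine", followed by the same dialysis and death components. Both attach Day 30 and Day 90. Neither says which value the creatinine must double from.

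**Analysis.** Section 9.4.3 gives the scoring rule: "MAKE is defined as Yes if a doubling of serum creatinine (from baseline), the initiation of long-term dialysis", or death from any cause. Of these definitions it is the only one that mentions a reference, and it does not date it. The proportional hazards model uses "time to the first occurrence of MAKE over the entire duration of the study from baseline to 90 days post-randomization". The doubling need not be confirmed, persist, or be present at the Day 30 or Day 90 visit. No section gives an operational rule for CKD development or progression.

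**Meaning of baseline.** The usual sense is Day 1. The Section 1.3 footnote reads "Baseline (Day 1) assessments should be performed prior to study drug administration", Section 2.3.1 measures laboratory change from Day 1, and Section 6.1.1 labels the Day 1 visit as baseline. A second sense appears in Table 3 (Section 5.1), which stages AKI as multiples of a baseline that must precede the AKI, and in Section 4.2, which refers to kidney function before admission.

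**The concern.** The objective, endpoint and analysis should describe the same event, and here they do not. Section 5.1 randomizes only participants whose AKI is sustained, so for those staged on creatinine the Day 1 value is already raised. Doubling again from there is a worsening of the acute injury. CKD after AKI is largely a failure to come back down, and a rule based on a further doubling does not see that.

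MAKE has consequences beyond this trial. Under Section 2.1, improvement in any one secondary outcome at p<0.2, with no significant increase in harm, would support a Phase IIb study. A positive trend at p<0.2 together with a significant NAD+ increase and no significant harm would support Phase III. The same section expects the secondary endpoints to help power later studies, and envisions the proportion with MAKE at Day 90 as the Phase III primary endpoint. Section 9.4.3 plans a hazard ratio and no Day 90 proportion. Section 2.3.3 names both less kidney injury and less CKD as the hoped-for benefit; the creatinine component speaks only to the first.

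**Working it through.** The plan states no MAKE event rate, hazard ratio, event count or power, so there is no MAKE figure to reproduce. The check is how the rule scores participants.

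**Inputs**
- Entry multiples of the staging reference (Table 3): Stage 1, 1.5 to 1.9; Stage 2, 2.0 to 2.9; Stage 3, 3.0 or more. These apply to participants staged on creatinine, not on urine output alone.
- Event multiple (Section 9.4.3): 2.0.
- Serum creatinine schedule: daily on Days 1 to 10, then Days 30 and 90 (Sections 8.1 and 9.4.3; Table 4).

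**Day 1 reading (better supported).** Let r be Day 1 creatinine divided by the staging reference. An event needs 2 × r times the staging reference.

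| Entry stage | r | Needed for an event | Staying at r to Day 90 |
|---|---|---|---|
| 1 | 1.5 to 1.9 | 2×1.5=3.0 to 2×1.9=3.8 | ratio to Day 1 = 1.0, not an event |
| 2 | 2.0 to 2.9 | 2×2.0=4.0 to 2×2.9=5.8 | ratio to Day 1 = 1.0, not an event |
| 3 | 3.0 or more | 2×3.0=6.0 or more | ratio to Day 1 = 1.0, not an event |

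Two constructed participants, each with a staging reference of 1.0, show the effect. They carry no frequency.
- *Never recovers:* Day 1 is 2.5 and Day 90 is 2.5. As written, 2.5/2.5 = 1.0, so No. Against the staging reference, Day 90 is 2.5/1.0 = 2.5.
- *Worsens, then fully recovers:* Day 1 is 1.5, Day 4 is 3.0, Days 30 and 90 are 1.0. As written, 3.0/1.5 = 2.0, so Yes at Day 4. Against the staging reference, Day 90 is 1.0/1.0 = 1.0.

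The two errors run in opposite directions.

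**Staging-reference reading (less supported).** The event condition is r ≥ 2.0. Stage 2 and Stage 3 entrants staged on creatinine meet it at time zero, including any who later recover. A Stage 1 entrant needs a further rise of 2.0/1.9 = 1.05-fold to 2.0/1.5 = 1.33-fold.

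**Sampling.** After Day 1 there are nine daily measurements (Days 2 to 10) and two later ones. Most opportunities to register a first doubling fall in the acute phase.

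On neither reading does the creatinine component classify CKD status at Day 30 or Day 90.

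**The case against.** **Baseline is not really ambiguous.** Day 1 is the document-wide usage, and Section 9.4.3 itself runs time from baseline and adjusts for baseline creatinine. This stands. A reader might infer that Stage 2 and 3 entrants are all events at randomization. The documents do not support that as the intended rule, because it rests on a staging table and background prose, not on an analysis instruction. The mismatch does not depend on it: the Day 1 reading is the one that misses non-recovery. Adjusting for baseline creatinine does not change who counts as an event.

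**Further injury is a legitimate outcome.** Section 2.3.3 lists less kidney injury among the benefits, and any first-event endpoint counts transient events. This also stands, and is why the planned Cox analysis should be kept. It does not make the result an answer to a CKD objective.

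**The endpoint text already says Day 30 and Day 90.** Those words could mean status at the visits. Coupled with time to first occurrence and the Section 9.4.3 window, they read more naturally as follow-up horizons.

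**Recovery has its own endpoint.** eGFR and proteinuria at Days 30 and 90 (Section 9.4.3) capture it and also qualify under the p<0.2 rule. A reader might infer that the decision on further trials cannot register recovery, or that it rests on MAKE. Neither is so. But that endpoint does not enter MAKE.

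**A Day 90 proportion can be derived later.** It can, because Day 30 and Day 90 creatinine is collected. Its definition would then be chosen with the data in view.

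**Conclusion.** The point holds as a mismatch between objective, endpoint and analysis in a secondary endpoint, and it should be corrected. On the better-supported Day 1 reading, the creatinine component detects worsening to at least 3.0 times the staging reference, and to 6.0 times or more for Stage 3 entrants. It does not detect persistence at the entry level. The conclusion assumes staging on creatinine; those staged on urine output alone may have no raised Day 1 value.

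Death and long-term dialysis are scored the same on any reference. Section 2.2 reports 120/1213 = 9.9% deaths in patients meeting the trial's criteria, with dates unknown. At that rate about 10 of 100 randomized participants would be events however creatinine is scored.

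A reader might want a figure for how far the MAKE proportion is off. The documents do not support one. The share scored differently cannot be derived, the two kinds of error partly offset, and the 44% not fully recovered at discharge in Section 4.2 comes from another cohort and time point. Confidence is high on the mismatch; no size in percentage points should be quoted.

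**What to change.** 1. Make the MAKE wording agree in Section 1.1, Table 2 and Section 9.4.3, and name the reference creatinine in Section 9.4.3.
2. Keep the planned Cox analysis, with its creatinine event labelled as doubling from Day 1 (AKI progression).
3. Add pre-specified Day 30 and Day 90 MAKE proportions by arm with 95% confidence intervals. Count death or long-term dialysis by that visit, or creatinine at that visit at least 2.0 times the reference used to stage AKI at eligibility. Report a threshold of at least 1.5 times (the Stage 1 lower bound) beside it, because 2.0 misses a Stage 1 entrant who stays at 1.5 to 1.9.
4. Record the staging reference value, its date and its source in the eCRF. Flag estimated references and run a sensitivity analysis without them. Use the multiple imputation already planned in Section 9.4.1 for missing visits.

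The cost is protocol and SAP wording plus the eCRF entry. Day 30 and Day 90 serum creatinine is already in Table 4, and using those visits avoids the fingerstick values taken after early discharge.

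There are three downsides. Some references will be missing, as Section 4.2 anticipates, and an in-hospital substitute may already be raised by AKI and so undercount events. With the 15% withdrawal and 5% attrition in Section 5.5, 1 − 0.85×0.95 = 19.25% to 15% + 5% = 20%, or about 19 to 20 of 100 participants, may need imputation. A creatinine multiple at a single visit remains a proxy for CKD.

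A smaller repair would be to write Day 1 into Section 9.4.3 and reword the objective as AKI progression. That removes the inconsistency, but leaves no pre-specified Day 90 proportion for planning Phase III.
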